- 5. Action taken regarding with study treatment.
- 6. Its outcome (not recovered/not resolved; recovered/resolved; recovering/resolving; recovered/resolved with sequelae; fatal; or unknown)

All adverse events must be treated appropriately. Treatment may include one or more of the following:

- Drug interrupted/withdrawn
- Concomitant medication or non-drug therapy given
- Patient hospitalized/hospitalisation prolonged
- No action taken (i.e. further observation only)

Conditions that were already present at the time of informed consent should be recorded in medical history of the patient.

Adverse events (including lab abnormalities that constitute AEs) should be described using a diagnosis whenever possible, rather than individual underlying signs and symptoms.

To ensure patient safety, every adverse event, occurring after the patient has provided informed consent and until end of the trial for each patient must be reported.

Adverse event monitoring should be continued for at least 30 days following the last dose of study treatment.

Abnormal laboratory values or test results constitute adverse events only if they fulfill at least one of the following criteria:

- they induce clinical signs or symptoms
- they are considered clinically significant
- they require therapy

Clinically significant abnormal laboratory values or test results must be identified through a review of values outside of normal ranges/clinically notable ranges, significant changes from baseline or the previous visit, or values which are considered to be non-typical in patients with the underlying disease. Alert ranges for laboratory and other test abnormalities are included in Section 16.1.

Once an adverse event is detected, it must be followed until its resolution or until it is judged to be permanent, and assessment must be made at each visit (or more frequently, if necessary) of any changes in severity, the suspected relationship to the study drug, the interventions required to treat it, and the outcome.

Information about common side effects already known about the investigational drug can be found in the Investigator Brochure (IB).

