10.1.2 Serious adverse events

An SAE is defined as any AE [appearance of (or worsening of any pre-existing)] undesirable sign(s), symptom(s) or medical conditions(s) which meets any one of the following criteria:

- is fatal or life-threatening
- results in persistent or significant disability/incapacity
- constitutes a congenital anomaly/birth defect
- requires inpatient hospitalization or prolongation of existing hospitalization, unless hospitalization is for:

- routine treatment or monitoring of the studied indication, not associated with any deterioration in condition (asthma)
- elective or pre-planned treatment for a pre-existing condition that is unrelated to the indication under study and has not worsened since signing the informed consent
- treatment on an emergency outpatient basis for an event not fulfilling any of the definitions of a SAE given above and not resulting in hospital admission
- social reasons and respite care in the absence of any deterioration in the patient's general condition
- is medically significant, e.g. defined as an event that jeopardizes the patient or may require medical or surgical intervention to prevent one of the outcomes listed above.

All new malignant neoplasms will be assessed as serious under "medically significant" if other seriousness criteria are not met.

Life-threatening in the context of a SAE refers to a reaction in which the patient was at risk of death at the time of the reaction; it does not refer to a reaction that hypothetically might have caused death if it were more severe (see Annex IV, ICH-E2D Guideline (2003)).

Medical and scientific judgment should be exercised in deciding whether other situations should be considered serious reactions, such as important medical events that might not be immediately life threatening or result in death or hospitalization but might jeopardize the patient or might require intervention to prevent one of the other outcomes listed above. Examples of such events are intensive treatment in an emergency room or at home for allergic bronchospasm, blood dyscrasias or convulsions that do not result in hospitalization or development of dependency or abuse (see Annex IV, ICH-E2D Guideline (2003)).

Any suspected transmission via a medicinal product of an infectious agent is also considered a serious adverse reaction.

All reports of intentional misuse and abuse of the product are also considered serious adverse event irrespective if a clinical event has occurred.

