12.5.1 Safety endpoints

Adverse events

All information obtained on adverse events will be displayed by treatment sequence and patient.

All treatment emergent AEs will be summarized and listed.

AEs starting on or after the time of the first inhalation of study drug and until 30 days after the last inhalation will be classified as a treatment emergent AE. Any AEs that started during the study after signing informed consent and before the time of the first inhalation of study drug will be classified as a prior AE and will not be included in tabulations of the treatment emergent AEs.

The following treatment emergent AE summaries will be produced:

- by treatment, system organ class and preferred term,
- by treatment, system organ class, preferred term and maximum severity

suspected drug-related AEs by system organ class and preferred term, SAEs by system organ class and preferred term, and AEs leading to discontinuation of study-drug by system organ class and preferred term.

The number and percentage of patients with the most frequent AEs will be summarized by treatment.

Vital signs

All vital signs data will be listed by treatment sequence, patient, and visit/time and if ranges are available, abnormalities (and relevant orthostatic changes) will be flagged. Summary statistics will be provided by treatment and visit/time.

12-lead ECG

PR, QRS, QT, QTcF, and RR intervals will be obtained from 12-lead ECGs for each participant during the study. ECG data will be read and interpreted centrally. All ECG data will be listed by treatment sequence, patientand visit/time, abnormalities will be flagged. Summary statistics will be provided by treatment and visit/time.

Clinical laboratory evaluations

All laboratory data will be listed by treatment sequence, patient, and visit/time and if normal ranges are available abnormalities will be flagged. Summary statistics will be provided by treatment and visit/time.

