#### 2.8.1 Adverse events (AEs)

All information obtained on adverse events will be displayed by treatment sequence and patient.

All treatment emergent AEs will be summarized and listed.

AEs starting on or after the time of the first inhalation of study drug and until 30 days after the last inhalation will be classified as a treatment emergent AE. Any AEs that started during the study after signing informed consent and before the time of the first inhalation of study drug will be classified as a prior AE and will not be included in tabulations of the treatment emergent AEs.

The following treatment emergent AE summaries will be produced:

- by treatment, system organ class and preferred term,
- by treatment, system organ class, preferred term, and maximum severity

Novartis	Confidential	Page 14 of 16
SAP Amendment 1		Study No. CQMF149G2203

suspected drug-related AEs by system organ class and preferred term, SAEs by system organ class and preferred term, and AEs leading to discontinuation of study-drug by system organ class and preferred term.

The number and percentage of patients with the most frequent AEs will be summarized by treatment.

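### Treatment emergence is decided by start time alone, so a screening AE that worsens after dosing drops out of the treatment-emergent summaries

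*SAP*

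**What the plan says.** SAP 2.8.1 counts as treatment emergent "AEs starting on or after the time of the first inhalation of study drug and until 30 days after the last inhalation". An AE that began after consent but "before the time of the first inhalation of study drug will be classified as a prior AE and will not be included in tabulations", meaning the treatment-emergent tables. Protocol 12.5.1 uses the same rule, opening with "AEs starting on or after the time of the first inhalation of study drug". Neither section mentions an AE that starts before dosing and gets worse afterwards.

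The planned tables follow the lead-in "The following treatment emergent AE summaries will be produced". Two bulleted summaries come next: by treatment, system organ class and preferred term, and the same with maximum severity. Then come the drug-related summary, "SAEs by system organ class and preferred term", and the summary of AEs leading to discontinuation. A separate sentence adds "The number and percentage of patients with the most frequent AEs will be summarized by treatment".

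On recording, protocol 10.1.1 asks for a severity grade and start and end dates for each AE. Once an AE has been detected, "assessment must be made at each visit (or more frequently, if necessary) of any changes in severity, the suspected relationship to the study drug", among other things. Protocol 10.1.2 begins its definition of seriousness with "An SAE is defined as any AE [appearance of (or worsening of any pre-existing)] undesirable sign(s), symptom(s) or medical conditions(s".

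**The concern.** A summary of treatment-emergent events should show what happened to the children after they inhaled study drug. Under a rule based only on start time, two children with the same post-dose deterioration are treated differently if one had a mild complaint before Day 1. Screening lasts up to 14 days and the population is children with asthma, so a minor complaint may be running at the first dose.

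The secondary safety objective concerns QMF149, and these tables are its main summary. The error can go only one way: a post-dose worsening may be left out, but none is added.

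**Working it through.** No arithmetic decides this point, since it is a classification rule. The check applies the rule as written to hypothetical records.

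**Which date counts?** Protocol 10.1.1 follows a detected AE to resolution or permanence and reassesses its severity along the way. That describes one continuing event with one start date. No section tells sites to open a new record when severity rises. Protocol 10.1.3 also attaches the progression of an SAE to the episode already reported. Its sentence on separate reporting concerns an earlier SAE, not a non-serious AE that later becomes serious.

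**Does another rule close the gap?** SAP 5.1.2 imputes partial AE dates and resolves uncertainty towards on-treatment. A screening AE with a complete start date involves no uncertainty, so that rule does not apply.

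**Applying the rule**

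| Record | Start date used | Class | Treatment-emergent summaries |
|---|---|---|---|
| Cough starts Day -3, mild; severe after the Day 6 QMF149 dose; one record | Day -3 | Prior AE | Out |
| Same cough, but it starts on Day 2 | Day 2 | Treatment emergent | In |
| Screening AE becomes serious after dosing; same record continued | Screening | Prior AE | Out |
| Screening AE becomes serious after dosing; worsening entered as its own event | Post-dose | Treatment emergent | In |

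The first two rows differ only in when the mild phase began, yet the severe post-dose cough is counted in one and not the other. The last two rows are the same clinical event, and only data entry separates them.

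**Which outputs are affected?** The system organ class and preferred term table and the maximum-severity table are bulleted directly under the treatment-emergent lead-in, so exclusion is explicit. The drug-related, SAE and discontinuation summaries are most naturally read as belonging to the same list, and no separate table of all SAEs is specified. The most-frequent-AE sentence, the special-interest search in SAP 2.8.1.1 and the death listing in SAP 2.8.2 carry no express treatment-emergent limit.

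**Size.** The expected number of omissions is N x p x q. Here N is the number of children dosed, p the proportion with a screening AE ongoing at Day 1, and q the proportion of those that worsen after dosing. The documents give neither p nor q, so no number follows. What does follow is the weight of one child: 1/24 = 4.2 percentage points at the completer target, or 1/32 = 3.1 points if all of the approximately 32 planned children are dosed.

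**The case against.** The strongest reply is that little is hidden. SAP 2.8.1 plans a display of all AE information by patient, deaths are listed, and protocol 10.1.3 requires SAEs to be reported within 24 hours from consent onwards, whatever the cause. Safety is descriptive in an open-label, single-dose PK study, with no safety hypothesis. This stands: a careful reader of the listings would find the case. It limits the consequence but does not correct the tables.

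A reader might infer that such an event is left out of every AE and SAE table. The documents do not support that, because several outputs have no express treatment-emergent limit. A reader might also infer that a serious worsening must be missing from the SAE table. That does not follow either: the SAE definition in protocol 10.1.2 covers worsening of a pre-existing condition, so the worsening can be entered as its own post-dose event. What remains is that nothing requires this.

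It is also tempting to attach a probability to an omission. Any such figure would rest on assumed rates. Exclusions 8 and 9 remove children with an active infection, or with an exacerbation needing systemic steroids, hospital admission or emergency care, in the six weeks before Day 1. Table 8-1 has eligibility rechecked on Day 1. Ongoing respiratory illness at the first dose should therefore be less common than in unselected children with asthma, although milder complaints remain possible.

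Finally, a worsening between Day 1 and Day 6 follows the Twisthaler dose only and says nothing about QMF149. CRF completion instructions and the programming specification are not among the documents and might settle the start-date question, but the plan does not rely on them for this definition.

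**Conclusion.** The rule needs a worsening criterion. For an AE that only increases in severity, exclusion from the treatment-emergent summaries follows from the text, given that the worsening stays on the existing record as protocol 10.1.1 describes. For an AE that becomes serious, exclusion is conditional on site practice, so similar cases could be tabulated differently.

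The number of events affected cannot be estimated from the documents and is probably small. The effect is a one-directional undercount in summary tables, not a loss of data. It still merits correction, because with so few children a single omitted event can turn a count of 1 into 0.

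**What to change.** In SAP 2.8.1, with protocol 12.5.1 aligned, define as treatment emergent any AE that starts on or after the first inhalation, or that starts before it and increases in severity or becomes serious on or after it, up to 30 days after the last inhalation. Keep the prior-AE class for events that start before the first inhalation and do not worsen.

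To implement this, have sites record a worsening as a new AE entry dated at the worsening. Assign that entry to the most recent treatment received, so that a change before the Day 6 dose counts under MF Twisthaler and a later one under QMF149.

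The cost is one clause in each document, a data-entry instruction and minor programming. Amending the protocol carries the approvals set out in protocol 14.1. If only the SAP is changed, SAP section 4, which now reports no change from the protocol, must state the difference. The downside is that some worsenings unrelated to drug will enter the tables and AE counts may rise slightly.

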#### 2.8.1.1 Adverse events of special interest

The Compound Case Retrieval Strategy (CRS) will be used to determine the MedDRA search criteria to be used to identify events of special interest. The most recent list of adverse events of special interest at the time of database lock will be used.

#### 2.8.2 Deaths

All deaths will be listed by patients.

#### 2.8.3 Laboratory data

All laboratory data will be listed by treatment sequence, patient, and visit/time and if normal ranges are available abnormalities will be flagged. Summary statistics will be provided by treatment and visit/time.

#### 2.8.4 Other safety data

#### 2.8.4.1 ECG data

PR, QRS, QT, QTcF, and RR intervals will be obtained from 12-lead ECGs for each participant during the study. ECG data will be read and interpreted centrally. All ECG data will be listed by treatment sequence, patient and visit/time, abnormalities will be flagged. Summary statistics will be provided by treatment and visit/time.

#### 2.8.4.2 Vital signs

All vital signs data will be listed by treatment sequence, patient, and visit/time and if ranges are available, abnormalities (and relevant orthostatic changes) will be flagged. Summary statistics will be provided by treatment and visit/time.

## 2.9 Pharmacokinetic endpoints

Refer to Section 2.5 and Section 2.7 for primary and secondary objectives related to PK endpoints.

## 2.10 PD and PK/PD analyses

Not applicable.

## 2.11 Patient-reported outcomes

Not applicable.

## 2.12 Biomarkers

Not applicable.

## 2.13 Other Exploratory analyses

Not applicable.

## 2.14 Interim analysis

An iterim analysis is planned to be performed when 12 patients complete both study tractment and there are at least 3 completers in each of the two age groups  $\geq 6$  to 9 < year olds and  $\geq 9$  to  $\leq 12$  year olds. The interim analysis will be based on preliminary PK and safety data. An estimate of the systemic exposure as measured by the PK parameter ratios (QMF149 Concept 1 Breezhaler® vs MF Twisthaler®) together with corresponding 90% confidence intervals will be calculated in order to enable early decision making (e.g., study termination due to having achieved the primary objectives). Rationale for study continuation may include measures such as a review of training procedure for inhaler use by patients or sample size re-estimation.

# 3 Sample size calculation

Approximately 32 patients will be recruited in order to obtain 24 completers in this study considering 25% of drop out rate. The sample size of 24 complete patients is considered to yield satisfactory precision in the estimation of the systematic exposure, as measured by the ratio of the PK parameter Cmax, AUC(0-6h) of QMF149 Concept 1 Breezhaler® vs MF Twisthaler®. With 24 complete patients, the 90% confidence intervals of the PK parameter (AUC (0-6h) and Cmax) ratios (QMF149 Concept 1 Breezhaler® vs MF Twisthaler®) are expected to be within 72% to 138% with 90% coverage probability. The calculation was based on an assumed 2-fold increase in variability in pediatric population compared to adults who showed intra-patient CV of 30% in the CQMF149E2101 study.

# 4 Change to protocol specified analyses

No change from protocol specified analysis was made.

# 5 Appendix

The sections below contain additional details on statistical methodology that will be included in Appendix 16.1.9 (Documentation of Statistical Methods) of the CSR as well as details on programming rules that will be followed to implement the analyses described in Section 2.

# 5.1 Imputation rules

## 5.1.1 Study drug

Missing/partial start date or end date of treatment will not be imputed.

## 5.1.2 AE date imputation

Partial AE start and end dates will be imputed. If there is uncertainty whether an AE occurred on-treatment or not, imputation will be performed, such that AE will be considered as on-treatment. Rules for imputing AE end date or start date will be provided in Programming Dataset Specification (PDS) document in details.

## 5.1.3 Concomitant medication date imputation

Rules for imputing the CM end date or start date will be provided in Programming Dataset Specification (PDS) document in details.

# 5.2 AEs coding/grading

The MedDRA version which will be available at the time of database lock, will be used for the coding purpose of the adverse events.

## 5.3 Laboratory parameters derivations

If laboratory values are provided as (<X') (i.e. below limit of detection) or (>X'), prior to conversion of laboratory values to SI unit, these numeric values are set to X.

## 5.4 Statistical models

#### 5.4.1 Primary analysis

Refer to Section 2.5.

## 5.4.2 Key secondary analysis

Refer to Section 2.7.

## 5.5 Rule of exclusion criteria of analysis sets

The following table provides the protocol deviations (PD) and other criteria leading to partial or complete exclusion from analyses sets.

Deviation ID	Description of Deviation	
Deviations leading to exclusion from all analyses sets		
INCL02	Informed consent was not obtained before any assessment.	
EXCL11	Parent or guardian has a history of psychiatric disease, intellectual deficiency, or substance abuse	

